While both routes are safe and routinely used by cardiac anesthesiologists at UVA, there are several proposed advantages to nasal intubation in the neonatal cardiac population. Firstly, nasotracheal tubes are more comfortable to the patient as well as more easily secured. Because of this, thus patient requires less sedation to prevent accidental extubation. Secondly, without an oral endotracheal tube in place, the infant is able to practice non-nutritive sucking skills in preparation for oral feeding. A study by Pinelli et al. (2005) showed that non-nutritive sucking helped premature infants more quickly transition from gavage to oral feeding. With lower sedation and oral skills development, we believe that nasally intubated patients will more quickly learn to orally feed and avoid the need for gastrostomy.

Objectives/Hypothesis

Hypothesis: Nasotracheal intubation will allow for lighter sedation in the post-operative period as well as more rapid development of oral feeding skills for infants with congenital heart disease.

Primary outcome measures:

1) Time from surgery to full oral feeds.

Secondary outcome measures:

- 1) Dosage of sedating medications required post-operatively.
- 2) Hospital length of stay.
- 3) Need for tube feeds at discharge (NG or gastrostomy).

Study Design: Biomedical

1. Will controls be used?

No. Participants will be randomized to an intervention - either oral or nasal intubation. All infants will be intubated for surgery, so there is not a control group.

► **IF YES, explain the kind of controls to be used.**

Answer/Response:

2. What is the study design?

Randomized control study

3. Does the study involve a placebo?

No, participants will receive either oral or nasal intubation, both routes are considered safe and acceptable in neonates.

► **IF YES, provide a justification for the use of a placebo**

Answer/Response:

Human Participants

Ages: <2 weeks at the time of surgery

Sex: Male and female

Race: All

Subjects- see below

1. Provide target # of subjects (at all sites) needed to complete protocol.

Version Date: 06/14/18

Page Number: 3 of 8

A sample of 40 neonates in each group, for a total of 80 neonates, is required to have sufficient statistical power.

2. Describe expected rate of screen failure/ dropouts/withdrawals from all sites.

We anticipate that 10% of neonates will be unobserved on the primary outcome due to post-operative complications including need for ECMO or CPR >5 minutes.

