3. How many subjects will be enrolled at all sites?

44 participants per group, for a total of 88

4. How many subjects will sign a consent form under this UVa protocol?

88 participants.

Inclusion/Exclusion Criteria

1. List the criteria for inclusion

- Patient is a neonate requiring cardiac surgery
- Patient is <2 weeks of age at the time of surgery
- Includes families who are educationally or economically disadvantaged
- Includes non-English speaking families

2. List the criteria for exclusion

- Patient has an estimated gestational age <37 weeks at the time of surgery
- Patient has known oro-facial or gastrointestinal anomalies
- Patient has known congenital or acquired devastating neurologic injury
- Patient was intubated for >5 days pre-operatively
- Patient required >5 minutes of CPR pre- or post-operatively
- Patient requires ECMO pre- or post-operatively
- Patient remains intubated two weeks post-operatively.
- Excludes infants >2 weeks of age at the time of surgery and other vulnerable populations including pregnant women, fetuses, prisoners, cognitively impaired

3. List any restrictions on use of other drugs or treatments.

None.

Statistical Considerations

1. Is stratification/randomization involved?

Yes.

► IF YES, describe the stratification/ randomization scheme.

Patients will be randomized to oral or nasal intubation using a block randomization scheme generated by a UVA statistician to generate equally sized oral and nasal groups. The concealment envelope with group assignment will be opened by the anesthesiologist, CRNA, or resident performing intubation at the time of surgery. After intubation, this intervention is impossible to blind. The research team and family will be able to see which group the patient is part of.

► IF YES, who will generate the randomization scheme?

Sponsor
 UVa Statistician. [name]
 UVa Investigational Drug Service (IDS)
 Other: Answer/Response:

2. What are the statistical considerations for the protocol?

The null hypothesis to be tested is that the mean number of days to full oral feeding is the same with oral or nasal intubation. The alternative hypothesis is two-sided, and states that the mean number of days until full oral feeds differs between oral and nasal intubation.

3. Provide a justification for the sample size used in this protocol.

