Preliminary data on 8 neonates yielded an average of 13.5 from surgery to NG tube removal, with a standard deviation of 11.7. With 40 participants per group, the two-sample t-test with unequal variances yields 80% power, with a 2-sided significance level of 5%, when the mean difference in time to oral feeding is 6 days. In this calculation, we assumed that the coefficient of variation is the same in the nasal and oral intubation groups, meaning that the within-group standard deviation is proportion to the mean. Allowing for 10% dropout/withdrawal yields a sample size of 44 per group, for a total of 88 participants.

4. What is your plan for primary variable analysis?

Initial analyses will use the two-sample t-test, and the associated confidence interval, to compare the groups. Secondary analyses of the primary outcome, the number of days until full oral feeding, will be based on negative binomial regression. In addition to providing an unadjusted comparison of the groups, the use of negative binomial regression will also allow us to estimate the difference between the groups adjusting for covariates, such as the RACHS score (estimates risk of cardiac surgery). While we anticipate that the randomization will balance the distribution of these covariates between the groups, the use of these covariates in a model can improve the precision in estimating the difference between the oral and nasal intubation groups.

5. What is your plan for secondary variable analysis?

A two-sample nonparametric test will be used to compare the average dosage of sedating medications required post-operatively. For hospital length of stay, analyses similar to those described above for days until full oral feeding will be used. The third secondary outcome is a binary variable, indicating the need for tube feeds at discharge. The chi-square tests will be used to compare the proportion of participants in each group requiring tube feeding at discharge.

6. Have you been working with a statistician in designing this protocol?

Yes

IF YES, what is their name?

[name]

7. Will data from multiple sites be combined during analysis?

No

INSTRUCTIONS: IF YES, answer the following questions

7(a). Does the study involve randomization?

Answer/Response:

IF YES, will randomization be done at each site or among sites?

Answer/Response:

7(b). Has the sample size calculation considered the variation among sites?

Answer/Response:

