longer time required for nasal intubation, then they will be orally intubated for patient's safety. These patients will remain in the study and will be analyzed in the oral intubation group. Intubation route does not affect the subsequent surgery.

The patient will arrive to PICU intubated. The electronic medical record will be used to collect data regarding surgical variables, post-operative sedation needs, and feeding outcomes. The treatment of these patients post-operatively will follow the standard of care PICU procedures, without differences based on study assignment. The post-operative protocols are described briefly here: Sedation needs are determined by standardized sedation scores and nursing protocols. Feeding advances are determined by standardized PICU protocol, with alterations based on RN and MD clinical assessment. The patient will be extubated when clinically appropriate, based on PICU MD assessment. After extubation, the patient is assessed by a Speech-Language Pathologist who determines the patient progress with oral feeding. Data will be collected through hospital discharge.

2. If this protocol involves study treatment, explain how a subject will be transitioned from study treatment when they have completed their participation in the study.

This protocol does not involve an experimental treatment. Both oral and nasal intubation are safe methods, and both are routinely used by the pediatric cardiac anesthesiologists at UVA. After intubation, the remainder of the infant's intra- and post-operative care will proceed by the standard of care. The subject will be extubated when clinically appropriate as determined by the PICU MD. If the patient requires emergent re-intubation while in the PICU, it will be performed orally. Patients who are re-intubated will remain part of the study as long as they do not meet other exclusion criteria (ex. Intubated >2 weeks, >5 min CPR, ECMO).

Subject Compliance with Study Procedures

1. Explain how the study team will monitor the subject for compliance with the study procedures.

The study anesthesiologists will perform the procedure. There is no need for the patient or family to comply.

2. Describe criteria for when a subject is considered to be non-compliant with study procedures.

There is no need for the patient or family to comply. All procedures are performed by the study team.

Bibliography

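### Optional efficiency gain: the lead t-test on days to full oral feeding leaves out the RACHS adjustment that the protocol already plans as secondary

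*Protocol*

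**What the plan says.** Statistical Considerations, item 4, sets the order of the primary-outcome analyses: "Initial analyses will use the two-sample t-test, and the associated confidence interval, to compare the groups". Everything else on that outcome is called secondary and rests on negative binomial regression, first unadjusted and then "adjusting for covariates, such as the RACHS score (estimates risk of cardiac surgery"). The reason given for adjusting is that "the use of these covariates in a model can improve the precision in estimating the difference between the oral and nasal intubation groups". The item says *initial*, not *primary*. Because all other analyses are labelled secondary and the sample size (item 3) is built on the t-test, reading it as the lead analysis is fair.

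Three other places bear on the point:
- Item 2 frames the test on the days scale: "The null hypothesis to be tested is that the mean number of days to full oral feeding is the same".
- Item 1 describes allocation: "Patients will be randomized to oral or nasal intubation using a block randomization scheme". Its stated purpose is equal group sizes, and no stratification factor is named. Item 4 relies on chance for the rest: "While we anticipate that the randomization will balance the distribution of these covariates between the groups".
- The Background cites a retrospective review of 83 infants in which a higher RACHS score was a risk factor for delayed transition from gavage to oral feeds. It gives no effect size for days.

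**The concern.** The protocol names a covariate that it believes to be prognostic for something very close to its primary outcome, and it states the benefit of adjusting. It then uses that covariate neither in the allocation nor in the comparison that will carry the conclusion. The trial is single-centre, enrols 88 neonates and aims to detect 6 days against a pilot mean of 13.5, so precision is scarce.

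The secondary adjusted model does not fully recover the benefit. The lead test and interval stay unadjusted, and a log-link model naturally reports a ratio of means, not the difference in mean days on which the null is written. At stake is the width of the lead confidence interval and some power, to an extent that depends on how strongly RACHS predicts days.

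**Working it through.** **Inputs from the protocol (Statistical Considerations, item 3).** Pilot mean 13.5 and SD 11.7 (8 neonates); difference 6 days; common coefficient of variation; 40 per arm analysed; two-sided 5%; unequal-variance t-test; stated power 80%.

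**Assumptions.** The protocol gives no R2 for RACHS and no RACHS case mix. R2 is taken from 0 to 30% of within-arm variance. The simulations use a five-level ordinal score with assumed shares 10/30/30/5/25%. The direction is taken as 13.5 against 7.5 days, because this reproduces the stated power.

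**Step 1: reproduce the plan's figure.** CV = 11.7/13.5 = 0.867, so the SD at 7.5 days is 0.867 × 7.5 = 6.5. SE = √[(11.7² + 6.5²)/40] = √4.4785 = 2.116 days. Noncentrality = 6/2.116 = 2.84. With Satterthwaite degrees of freedom, noncentral-t power is 79.7% and the 95% half-width is 4.23 days. The stated 80% is reproduced.

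**Step 2: simple analytic effect of adjustment.** SE(adjusted) = √[(1 − R2) × 4.4785]. At R2 = 20% this is √3.583 = 1.893 days, giving 87.7% power. This is optimistic: it treats one common slope as capturing the whole R2 and charges nothing for estimating that slope or for HC3.

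**Step 3: simulation.** 20,000 runs per cell, complete data, negative binomial (NB) or log-normal (LN) days with CV 0.867 in each arm and RACHS acting multiplicatively. Welch's t-test is compared with a linear model (arm plus one linear RACHS term, HC3, 77 df). Simulated Welch power is 83–84% (NB) and 85–86% (LN), above the analytic value because the data are skewed. The net changes below also cover smaller repeat runs.

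| R2 | Analytic SE (days) | Analytic power | Adjusted power, NB | Adjusted power, LN | Net change (points) | Equivalent unadjusted infants per arm | Half-width, NB (Welch 4.2 days) |
|---|---|---|---|---|---|---|---|
| 0% | 2.12 | 79.7% | 82% | 85% | about -1 | 39 | 4.27 |
| 5% | 2.06 | 81.7% | 84% | 86% | 0 to +1 | 41 | 4.16 |
| 10% | 2.01 | 83.7% | 86% | 88% | +2 to +3 | 43 | 4.07 |
| 20% | 1.89 | 87.7% | 89% | 91% | +6 | 47 | 3.86 |
| 30% | 1.77 | 91.5% | 93% | 94% | +9 | 53–54 | 3.64 |

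**Step 4: how the gain depends on form.**
- If only the top RACHS level is slower, the linear term gains about 0, +1, +4 and +6 points at R2 of 5, 10, 20 and 30%.
- RACHS entered as categories gives about -4, -2, 0, +4 and +7 to +8 points at 0, 5, 10, 20 and 30%. Break-even is near 10%, against about 5% for the linear term.
- A separate run with gamma days and four levels gained under 1 point at a sample R2 of about 8%.

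**Step 5: type I error (13.5 against 13.5 days).** Linear term with HC3, 3.9–4.7%; categories, 3.6–4.3%; Welch, 4.3–4.9%. The unadjusted negative binomial Wald test gives 5.6% on NB data and 10.8% on LN data.

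**The case against.** The strongest reply is that nothing here is wrong. The null, the sample size and the lead test all concern unadjusted mean days and agree with one another. An unadjusted lead test with an adjusted secondary is an accepted choice, and a RACHS-adjusted result will be reported anyway. The one cited study gives no effect size for days. The exclusions (ECMO, long CPR, still intubated at two weeks) may narrow the range over which RACHS predicts anything. Up to R2 of 10% the change is only -1 to +3 points, and nothing in the documents supports 20–30%. All of this stands, and it is why the point is optional.

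It does not remove the point. The order of analyses is written into the protocol, so it is a stated choice and not a detail left to an analysis plan. The trade is also lopsided: about 1 point lost if RACHS is useless, several gained if it is moderately prognostic.

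Four stronger readings are tempting, and the documents do not support them:
- *The t-test is invalid or the trial is underpowered because it ignores RACHS.* The test is valid under randomisation and meets its stated power.
- *Unstratified allocation biases the comparison.* With 40 per arm, mean RACHS differs by more than 0.3 SD in 2 × [1 − Φ(0.3/√(2/40))] = 18% of trials. At R2 = 20% that moves the unadjusted difference by 0.3 × √0.20 × (11.7 + 6.5)/2 = 1.2 days. This is the same precision loss seen within one trial; it is neither a bias nor a second harm.
- *The planned negative binomial model should simply be promoted.* It changes the effect measure, and its Wald test can exceed 5% (step 5).
- *The gain disappears if long-stay infants go unobserved.* The protocol says "We anticipate that 10% of neonates will be unobserved on the primary outcome" and "Data will be collected through hospital discharge", so such losses are possible, but their effect depends on the pattern. Dropping the four longest times per arm shrinks the change to between -1 and +4 points. An assumed common cut-off at day 20 gives 74% for Welch and 79% adjusted at R2 = 10%. No general limit follows.

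**Conclusion.** The point holds as an optional efficiency gain. The protocol forgoes a cheap precision gain in its lead comparison, conditional on RACHS being prognostic. With 40 per arm the change in power is about -1, 0 to +1, +2 to +3, +6 and +9 points at R2 of 0, 5, 10, 20 and 30%, from an unadjusted 79.7% analytically or about 83–86% in skewed simulations. Below an R2 of roughly 5–8% the gain is negligible.

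These figures rest on an assumed R2 and RACHS case mix, the 13.5 against 7.5 day scenario, complete data and intact randomised arms. How undischarged feeding outcomes and failed nasal intubations are handled is a separate matter that either analysis would inherit.

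**What to change.** In Statistical Considerations, item 4, define the primary comparison as the oral–nasal difference in mean days from a linear model with arm and one prespecified RACHS term, using HC3 standard errors and a t reference. Enter RACHS as a single ordinal score fixed from information available before randomisation, not as categories, and close the open list of covariates for this model. Keep the two-sample t-test and the negative binomial model as supporting analyses. The null in item 2 and the days scale stay as they are, and the sample size need not change.

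The cost is protocol wording. RACHS is already planned for analysis, so no extra infants are needed, and no new data provided the score can be fixed before randomisation. The downside is about 1 point of power if RACHS is uninformative (about 4 if it is entered as categories) and a slightly conservative test, 3.9–4.7% at a nominal 5%.

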Skinner et al. (2005) conducted fiberoptic laryngoscopy in 33 neonates after Norwood single ventricle palliation compared with 18 infants after aortic arch reconstruction as part of biventricular repair. In the Norwood group, 48% of infants had some degree of swallowing dysfunction. 9% of Norwood infants were diagnosed with left vocal cord paralysis, 24% had aspiration on barium swallow, and 18% of infants required gastrostomy tube placement for feeding. In the aortic arch reconstruction group, 25% of infants were diagnosed with left vocal cord paralysis, 35% had aspiration on barium swallow, and 11% required gastrostomy tube placement for feeding. They concluded that vocal cord paralysis and aspiration occur in similar frequencies in neonates regardless of single or biventricular repair.

Both oral and nasal intubation routes are considered safe and acceptable in neonates. However, there have been only a few head-to-head trials to compare the two routes to each other in this population. Spitzer et al. (1982) conducted a trial of 86 neonates requiring intubation for mechanical ventilation. Infants were randomized to oral or nasal routes of intubation. The study found that nasally intubated infants had higher rates of post-extubation atelectasis. However, after accounting for weight, they found that the higher risk of post-extubation atelectasis was only present in infants < 1500 grams. Infants > 2500 grams (term size) were not at higher risk of post-extubation atelectasis. There was not a difference in the risk of local trauma (nasal erosions for nasal intubation, palatal groove formation for oral intubation) between groups. McMillan et al. (1986) conducted a trial of 91 neonates requiring intubation for mechanical ventilation. Infants were randomized to oral or nasal routes of intubation. In this study, nasal intubation was unsuccessful in 6 patients, who were subsequently successfully orally intubated without complications. They did not find increased risk of post-extubation atelectasis, endotracheal tube blockage, or accidental extubation in nasal compared to oral routes of intubation.

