7(c). When combining the data from multiple sites to assess the study results, is the effect of the treatment to be tested (or the association to be tested) assumed to be the same across sites or vary among sites? What is the modelling strategy?

Answer/Response:

7(d). Is there a common protocol used in all sites?

Answer/Response:

IF NO, how will differences among sites, such as those related to the implementation, inclusion criteria, patient characteristics, or other sites characteristics, be considered to assess the study results?

Answer/Response:

Study Procedures-Biomedical Research

1. What will be done in this protocol?

Potential subjects will be identified in the weekly Pediatric Cardiothoracic surgical conference. Subjects' parents will be approached as part of routine pre-operative discussions regarding surgical timing and post-operative expectations. Parents will be introduced to the study, and consented at that time. This will typically take place in the week before surgery, barring emergent changes to the surgical schedule.

Neither oral nor nasal intubation are done purely for research purposes in this protocol. Intubation is a standard and necessary part of the planned cardiothoracic surgery. The cardiac anesthesiologists and CRNAs are experienced in both methods. Typically, the decision of which route is based on clinician decision after assessing the patient. Studies by Spitzer (1982), McMillan (1986), and Xue (2007) demonstrate that both routes are safe in children. Any neonatal intubation carries risk of local trauma, desaturation, and bradycardia. The additional risk of oral intubation is palatal grooving. The additional risks of nasal intubation include nasal ulcers and the possibility of post-extubation atelectasis in infants <1500 grams. Nasal intubation takes slightly more time than oral intubation.

After enrollment, the patient will be randomized with assignment in a sealed envelope. On the day of surgery, the envelope will accompany the patient to the operating room. The anesthesiology team will open the envelope and proceed with the assigned intubation method (oral or nasal). The CRNA or anesthesiologist will intubate using the UVA standard of care. If nasal intubation is complicated by unexpected anatomy (such as choanal atresia), or if the patient cannot tolerate the

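### Infants randomised to nasal intubation but converted to oral are analysed as oral, so the planned comparison is not the randomised one

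*Protocol*

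**What the plan says.** Study Procedures item 1 describes two triggers for conversion to the oral route: anatomy that comes to light only at the attempt, and an infant who cannot bear the extra time. On the second it reads: "longer time required for nasal intubation, then they will be orally intubated for patient's safety". The analysis rule follows at once: "These patients will remain in the study and will be analyzed in the oral intubation group".

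Three other places bear on this.

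- Statistical Considerations item 1 uses a "block randomization scheme generated by a UVA statistician to generate equally sized oral and nasal groups".
- Item 4 compares the groups by t-test, does not define them further, and supports the covariate-adjusted model with "While we anticipate that the randomization will balance the distribution of these covariates between the groups".
- Item 3 gives the power: "With 40 participants per group, the two-sample t-test with unequal variances yields 80% power", for a 6-day difference at a two-sided 5% level. It makes no allowance for conversions.

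Conversion was foreseeable. The Background cites a randomised trial of 91 ventilated neonates in which "nasal intubation was unsuccessful in 6 patients, who were subsequently successfully orally intubated without complications".

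**The concern.** The analysis group is settled after randomisation, by something that happens to the infant, and in one arm only. By randomisation, infants who could not be intubated nasally should be equally common in both arms. In the oral arm nobody discovers who they are. In the nasal arm they are discovered and moved.

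The decision to convert is made by the team that has opened the envelope, and intolerance of the longer procedure has no stated criterion. Membership of the analysed groups therefore depends partly on judgement made with the allocation known.

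Both triggers could be related to recovery and feeding.

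- If these infants feed later than average, the rule creates an apparent nasal advantage, which is the direction of the hypothesis.
- If they feed sooner, it creates an apparent oral advantage.
- If their prognosis is average, there is no bias.

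The trial's own data could not settle which applies, because the oral-arm counterparts are not identified. The rule affects the primary outcome and every secondary outcome. The decision to convert for safety is not in question.

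**Working it through.** **Inputs from the protocol.** 40 analysed per group, two-sided 5%, 6-day difference, pilot mean 13.5 and SD 11.7, common coefficient of variation (Statistical Considerations item 3). CV = 11.7/13.5 = 0.867.

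**Assumptions.** f is the share of infants who cannot be intubated nasally, equal in both arms. δ is their mean extra time to full oral feeds. The protocol gives no δ. For f, the cited trial had 6 failures: 6/91 = 6.6% of all its infants, or 6/45.5 = 13% of the nasal arm if the arms were equal, which is itself an assumption. The rate may be lower here, because infants under 37 weeks and those with known oro-facial anomalies are excluded.

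**1. The stated power.** Means 13.5 and 7.5, SDs 11.7 and 0.867 × 7.5 = 6.5. The standard error is √[(11.7² + 6.5²)/40] = 2.116, and 6/2.116 = 2.84. The noncentral t with Satterthwaite degrees of freedom (61) gives 79.7%, so the stated 80% reproduces.

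**2. Bias under the protocol's rule, with no route effect.** Let other infants have mean m.

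- The analysed nasal group contains only other infants, so its mean is m.
- The analysed oral group has n + nf infants, of whom nf + nf = 2nf are of the difficult kind. Its mean is m + δ·2f/(1+f).
- Oral minus nasal is therefore δ·2f/(1+f). For f = 13% and δ = 11.7: 11.7 × 0.26/1.13 = 2.7 days.

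**3. Type I error.** 20,000 simulated trials per case, 40 per arm, gamma-distributed times with overall mean 13.5 and CV 0.867, no route effect, Welch test:

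| f | δ (days) | Spurious difference (days) | Type I error, protocol's rule |
|---|---|---|---|
| 2%, 5% or 13% | 0 | 0 | 5% |
| 2% | 11.7 | 0.5 favouring nasal | 5% |
| 5% | 6 | 0.6 favouring nasal | 5% |
| 5% | 11.7 | 1.1 favouring nasal | 6% |
| 6.6% | 6 | 0.7 favouring nasal | 5.9% |
| 6.6% | 11.7 | 1.4 favouring nasal | 7.4% |
| 13% | 6 | 1.4 favouring nasal | 8% |
| 13% | 11.7 | 2.7 favouring nasal | 15% |
| 13% | −6 | 1.4 against nasal | 7% |

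Analysed as randomised, the type I error stayed between 4.4% and 5.1%. That assumes all 40 per arm are observed.

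**4. Group sizes.** Nasal 40(1−f), oral 40(1+f): 38 and 42 at f = 5%, about 35 and 45 at f = 13%.

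**5. Power if analysed as randomised.** Assume a 6-day effect of the route received and δ = 0. The nasal-arm mean is 13.5 − 6(1−f). Its variance is (1−f)(6.5² + 7.5²) + f(11.7² + 13.5²) minus the squared mean.

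| f | Nasal-arm mean | Nasal-arm SD | Difference (days) | Power, 40 per group | n per group for 80% |
|---|---|---|---|---|---|
| 0 | 7.5 | 6.5 | 6.0 | 79.7% | 41 |
| 2% | 7.62 | 6.70 | 5.88 | 77.5% | 43 |
| 5% | 7.80 | 6.98 | 5.70 | 74.1% | 47 |
| 13% | 8.28 | 7.66 | 5.22 | 64.3% | 58 |

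The group sizes are before the dropout allowance. Simulation with gamma data gives somewhat higher power: 84% at f = 0, 77–78% at f = 5% and 66–67% at f = 13%.

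**The case against.** The strongest objection is size. At f of 5% or less the type I error is at most about 6%, even with a prognosis gap of a full standard deviation. The 15% needs the top of the range for f and that gap together, and nothing in the protocol supports any particular δ. This stands: the case rests on the rule being unsound, not on a demonstrated large bias.

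Second, the statements on block randomisation and covariate balance describe allocation and an expectation, so the rule does not flatly contradict them. That is fair as to wording. Both properties are nevertheless relied on for the groups that are compared, and neither carries over once infants are moved.

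Third, the hypothesis concerns the tube's physical effect (a mouth free for sucking, lighter sedation), so route received is the exposure of interest. This explains the rule but does not remove the selection.

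Fourth, the stated power is not wrong under the plan's own rule. With δ = 0 and a 6-day effect, simulated power by route received stays at about 84% whether f is 0 or 13%. This is correct: the loss of power comes with the remedy.

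Finally, the exclusions for post-operative ECMO, prolonged CPR and intubation at two weeks also remove infants after randomisation, so analysis by assignment does not by itself restore the full randomised set. That is true, but it is a separate issue and does not make the regrouping rule sound.

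**Conclusion.** The concern holds. The protocol states an explicit one-way regrouping rule, nothing elsewhere overrides it, and the comparison planned for every outcome is therefore not the one formed by randomisation.

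The size cannot be fixed from the document. Over the assumed range (f from 2% to 13%, δ from −6 to 11.7 days) the spurious difference runs from 1.4 days against nasal to 2.7 days in its favour, set against a target effect of 6 days. The type I error runs from 5% to 15%. It is nil if converted infants have average prognosis and small if conversion is rare. Because the result could not separate a route effect from this selection, the rule should be corrected before analysis.

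**What to change.** In Study Procedures item 1, replace the sentence on the analysis group with: *These patients remain in the study and are analysed in the group to which they were randomised (nasal).* Apply this to the primary and all secondary outcomes. Keep the analysis by route received as a labelled sensitivity analysis, and report the number of conversions with the reason for each.

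In Statistical Considerations item 3, add that, with analysis as randomised, the 80% holds only if conversion is negligible, or give the power for an assumed conversion share.

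The wording costs two sentences and no extra data. The real cost is dilution: either accept about 74% power at 5% conversion and 64% at 13%, or raise the analysed number from 40 to about 47 or 58 per group (about 43 at 2%), before the dropout allowance.
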